## **A. SIGNIFICANCE**

**A1. HIV infection disproportionately affects the Southern U.S. with continuing inequities in rates among Black cis-gender women.** Despite advances in antiretroviral therapy (ART), rates of HIV infection have increased among highly disenfranchised populations, accentuating health disparities. Black people comprise only 13% of the U.S. population, but account for more than half of new HIV diagnoses. Adverse HIV outcomes are also higher, as Black people are less likely to be linked to or retained in care, contributing to lower rates of viral suppression and higher mortality. Notably, Black cis-gender women account for 57% of all new infections among women and the majority occur in those of reproductive age. These health inequities are most pronounced in the U.S. South. Despite comprising only a third of the U.S. population, the South accounts for nearly half of all new HIV infections, with the highest infection and mortality rates among Black populations. Furthermore, rural communities in the South have higher HIV infection rates, requiring targeted prevention strategies to address their unique cultural and structural barriers. This is especially true in Alabama, where rural counties have the highest rates of new HIV infections per 100,000 persons. Additionally, information-based HIV prevention interventions are less effective due to poverty, income and social inequality due to institutional racism. This is reflected in Alabama's local HIV epidemiology as Black cis-gender women are eight times more likely to be diagnosed with HIV compared to White women.

**A2. PrEP is an effective biomedical prevention strategy for HIV infection, but underutilized by cis-gender women.** Almost two-thirds of people prescribed PrEP are White and, of the 468,000 cis-gender women with a PrEP indication, only 19,000 (4%) are currently receiving prescriptions. Our university-affiliated infectious diseases-led PrEP Clinic in Alabama mirrors national trends in PrEP prescriptions, providing services for primarily White men who have sex with men (63% of clientele) with only 7% of our clientele being cis-gender women. Additionally, most studies evaluating PrEP uptake among cis-gender women have demonstrated that cis-gender women who access PrEP are mostly sero-discordant relationships with virally suppressed partners and, therefore, have minimal risk of transmission. Cited barriers for low uptake of PrEP among cis-gender women in the U.S. include: daily regimen, stigma from providers and peers, and perceived difficulty negotiating PrEP use with partners. However, these national studies may not be reflective of knowledge, attitudes and beliefs of cis-gender women living in Southern communities with unique social and structural determinants of health. This supports the need for theory-driven studies that focus on enhancing uptake of PrEP among cis-gender women living in the South where access to PrEP services has been limited at best. Theory-driven studies that focus on enhancing uptake of PrEP among cis-gender women living in the South are critically needed, given the dearth of studies focused on increasing uptake of PrEP in this population with inequitable rates of HIV infection. Additionally, this research would provide insight into implementing PrEP into a unique clinical setting, as to date research has focused on integration of PrEP into family planning care and sexually transmitted disease clinics for cis-gender women.

**A3. Clinical care settings focused on women's health may be ideal for PrEP service delivery among cis-gender women.** Given the inequities in PrEP prescriptions among Black cis-gender women, there has been growing literature on how to optimize uptake among this underserved population. However, there have been a dearth of studies that have focused on resource-limited settings like the Southern U.S. Studies conducted within this setting have shown that Black cis-gender women were willing to use PrEP; however, limited uptake has been reported. Safety-net programs created for cis-gender women to receive reproductive healthcare, like family planning clinics, have been evaluated in Southern states as sites for PrEP implementation. Women recruited from family planning clinics reported preferring PrEP information to be delivered through advertising and conversations directly with providers, as well as focused on awareness and access. Additionally, investigators working to implement PrEP in such settings noted low PrEP knowledge as a significant provider-level barrier, resulting in deployment of PrEP informational trainings in family planning clinics located in Southern states (including Alabama) to improve PrEP knowledge. But, even in this implementation study that focused on addressing client- and provider-level barriers through deployment of evidence-based implementation strategies, only 18% of patients seen (67 out of 376 sexually active cis-gender women) accepted off-site PrEP referral purportedly preferring to seek services on-site in the family planning clinic. In another study conducted in Washington D.C. at a family planning clinic where PrEP was offered on-site, again provider knowledge and PrEP referral increased with provider trainings, but uptake was sub-optimal with only 6% of those referred using PrEP. These studies provide proof of concept that general practitioners who specialize in women's health are able to gain foundational knowledge about PrEP indications for cis-gender women, but uptake was still limited and further research is needed on how to integrate PrEP care into routine women's health visits to improve PrEP uptake.

**A4. In the state of Alabama, gynecology clinics may provide an ideal setting for PrEP service delivery tailored for cis-gender women, in a state where family planning clinics are not currently prescribing PrEP.** There are limited settings that offer specialized care focused on women's health, like family planning clinics. However, *currently family planning clinics within the state of Alabama (AL) are not offering PrEP; furthermore, only one health department in Jefferson County, the county seat of Birmingham and the most populous county in AL, is providing PrEP services, limiting publicly-funded settings for cis-gender women to receive PrEP around the State.* Similar barriers are likely to be found in other Southern states with similar restrictive policies. Therefore, additional clinical settings that offer routine women's healthcare need to be identified as potential sites for PrEP service implementation. There is strong evidence to support that many women in the U.S. are seeking routine annual care for reproductive health and nearly half access only reproductive healthcare services. While family planning clinics provide much needed reproductive and sexual health services for many women (especially for those un- or under-insured), they only reach about one-quarter of U.S. women presenting for such care. Additionally, 81% of patients seen by gynecologists are of reproductive age (18-44 years), which also reflects the age range with greatest risk for HIV acquisition among cis-gender women.

**A5. Refining an approach to implement PrEP in gynecology clinics grounded in the RE-AIM (Reach, Effectiveness, Adoption, Implementation, and Maintenance) framework.** RE-AIM has robust support for its use in planning implementation as well as monitoring programs. RE-AIM has been used in program implementation research studies to focus and engage all stakeholders in decision making as well as provide a framework for evaluation. RE-AIM consists of five elements: 1) Reach (individual-level) – the ability to engage the target population in the intervention, 2) Effectiveness/Efficacy (individual-level) – evaluating the effect of the intervention on the primary outcome as well as the effect modification, 3) Adoption (setting-level) – determining the ability of the setting's staff to adopt the intervention, 4) Implementation (setting-level) – the extent to which the intervention was delivered as intended, AND 5) Maintenance (both individual- and setting-level) – evaluating the impact the finished intervention has on participants over time as well as the extent that the intervention is retained after the research period. There is also precedent to evaluate PrEP implementation at a family planning clinic in Washington, D.C., using the RE-AIM framework to evaluate feasibility and impact. Through utilization of this framework, the investigators identified the following: 1) facilitators included provider training, job aids to guide easy identification of guidelines for PrEP recommendation, order sets, documentation aids, educational materials in the waiting room and 2) barriers included lack of insurance and concerns among providers that discussing PrEP in such a setting may not be "patient-centered" especially for those seeking pregnancy termination. This proposal will focus on the initial planning stages, working with key-stakeholders and Black cis-gender women to assess *Reach, Adoption and preliminary Effectiveness* of integrating PrEP services within a gynecology clinic in Birmingham, AL providing women's healthcare to underserved, Black cis-gender women with the ultimate goal of increasing uptake of PrEP.

## **B. INNOVATION**

**B1. Overcoming the purview paradox – integrating PrEP into routine GYN care.** The "purviewparadox" was initially described as a major theme from qualitative data, suggesting that patients may prefer to receive PrEP services from primary providers instead of HIV specialists. However, there are limited studies evaluating implementation of PrEP with gynecologists who often are the primary providers for cis-gender women. National data evaluating willingness to prescribe PrEP showed that GYN providers are more willing to prescribe PrEP compared to general practitioners. *Our GYN pilot site is a large center that sees over 17,000 cis-gender women annually who reside across the state, in both urban and rural areas.* Forty percent of patients seen are Black cis-gender women, with the majority of reproductive age. (See Letter of Support) Prior work at UAB has shown cis-gender women seeking routine care are largely under-recognized as benefiting from PrEP prescription and, to date, no patients seen at the pilot facility have been prescribed PrEP. Implementing PrEP for cis-gender women as a part of routine sexual and reproductive health would also be unique, in that our team will not focus solely on women peri-conception. Given the pilot site's Southern location and patient population served, preliminary results from this pilot will provide substantial guidance on successful refinement and implementation of PrEP4Her in similar clinical-care settings across the South.

**B2. Development of a patient-centered implementation strategy, supported by end-user data to deliver PrEP services where, when, and how cis-gender women are most comfortable in engaging in the conversation.** Because demand for PrEP among populations with the highest HIV incidence is low, there has been a push to increase awareness of PrEP through development of demand creation tools, which focuses on strategies related to successful marketing campaigns, empowerment branding, and creation of different PrEP

delivery modalities (e.g. long-acting). These initiatives are crucial in improving HIV inequities. Such techniques are often “human-centered”, focused on the end-user working with researchers to develop interventions and improve implementation strategies. In fact, preliminary research, utilizing discrete choice experiments to understand PrEP service delivery preferences among Black cis-gender women, has also provided a foundation for PrEP4Her to be patient-centered. Additionally, this research actively engaged the community, through partnerships with community-based organizations, to adequately understand barriers to PrEP uptake and desired attributes for PrEP services. However, PrEP4Her will be focused on the equally important barrier to increasing PrEP uptake (i.e. supply creation) by improving access and expanding provider options for those that may benefit from using PrEP as an effective HIV prevention tool. Both end-user demand and health system supply creation will be necessary to overcome the current “prevention crisis” we are facing attuned to the “purview paradox,” in our goals to end the HIV epidemic and this study uniquely expands supply-side options.

**B3. Using implementation science methods to develop a clear understanding of optimal provision of PrEP services within the GYN clinic.** PrEP is a proven, highly effective intervention to decrease HIV transmission in cis-gender women. However, its impact to decrease HIV transmission among cis-gender women has been hindered due to a poor understanding of how to effectively identify strategies to improve uptake. Our proposed implementation science study is grounded in a conceptual implementation research logic model that includes implementation outcomes drawn from the RE-AIM and Proctor outcomes framework. Additionally, our study design includes evaluation of determinants for successful implementation of PrEP4Her by incorporating study aims to determine individual-, inner- and process-factor domains from the Consolidated Framework for Implementation Research (CFIR). In order to see public health gains from utilization of PrEP in real-world settings, more implementation science studies are needed with clearly outlined and reproducible methods, like what we have proposed in this grant.

## C2. Preliminary Studies

**Utilization of behavioral economics methods to understand Black women's preferred PrEP care delivery models.** Research on medical decision-making has increasingly used discrete choice experiments to evaluate intervention development for prevention tools, including HIV testing and the HPV vaccine. We conducted a mixed-methods study to understand key barriers, facilitators and desired attributes for PrEP service delivery among Black cis-gender women living in both urban and rural counties with high HIV burden in AL. Focus groups provided major determinants for PrEP uptake and attributes to include in quantitative analyses. *Discrete choice analyses included five attributes with 3-6 levels each, including PrEP delivery: modality, location, provider, medication/refills, and office intervals (Figure 1).* Hierarchical Bayes modeling was used to ascertain preferences. Of the 795 Black cis-gender women enrolled, the mean age was 35 and 28% were PrEP eligible based on CDC clinical guidelines. Nine percent were uninsured and about one-quarter had a household income <\$25,000. Approximately 30% (n=235) reported being willing to use PrEP, which was associated with higher HIV knowledge and perceived need. Average utilities were highest for PrEP services delivered in a doctor's office (27.9, SD 34.2), by an OB/GYN (8.9, SD 26.5) and only having annual follow-up (29.3, SD 49.0). PrEP modality preferences were almost the same for a long-acting injectable (46.9, SD 64.0) versus a once daily pill (45.0, SD 89.5). Major PrEP service delivery preferences did not differ among urban and rural Black cis-gender women. *(under review) Informed by this innovative science to understand PrEP service delivery preferences for Black cis-gender women living in both urban and rural settings in the South, PrEP4Her has the potential to reach a greater proportion of women and change routine practice among gynecology specialists through implementation of PrEP services.*

Figure 1. Hierarchical Bayes Analysis of PrEP Service Delivery Preferences (including 2 prominent attributes) among Black Cis-Gender Women

## C3. Research Design and Methods

[figure not shown]
**Study Overview:** We will conduct formative work, evaluating multi-level determinants that will inform selection of components for our implementation strategy to improve PrEP services including prescription for Black cis-

gender in the South receiving routine gynecologic care. Determinants will be evaluated using concurrent mixed-methodology to elucidate CFIR domains, including individual-, inner-setting, and process-level factors that may affect proximal, implementation outcomes. Working closely with a community-advisory board (CAB) of Black cis-gender women and key stakeholders at gynecology (GYN) clinics, we will solicit feedback about PrEP4Her implementation strategy components and procedures for the purposes of determining and refining PrEP4Her prior to piloting. Next, we will conduct a one-arm pilot study of PrEP4Her over a six-month period-of-time. Using the conceptual framework grounded in RE-AIM, the study will assess a wide range of implementation outcomes, including reach, adoption, preliminary effectiveness, feasibility, acceptability, and fidelity.

**Hypothesis:** We hypothesize that integration of PrEP services into our GYN clinic site will be feasible and acceptable, with an increase in PrEP prescription (currently zero prescriptions) for Black cis-gender women due to this being an initial pilot requiring further refinement of components included in our implementation strategy.

**PrEP4Her Implementation Science Research Logic Model:** This study is grounded in the RE-AIM framework to successfully implement PrEP into gynecologic (GYN) care that is cohesively organized by an implementation science research logic model. (**Figure 2**) Our logic model has been adapted to provide clear representation of the causal pathways between components of our implementation strategy (i.e. methods to enhance implementation of PrEP in GYN settings in the South), change mechanisms (i.e. the process through which implementation strategies affect implementation outcomes) and proximal outcomes for the proposed intervention (i.e. PrEP4Her, implementing PrEP into women's health clinics). Our model also includes hypothesized factors, selected based on our preliminary work and review of the literature, that may influence the effect of an implementation strategy on an outcome (i.e. moderators) as well as factors deemed necessary for implementation mechanisms to be activated (i.e. preconditions for mechanisms of action). This comprehensive model will help us select key components for our implementation strategy that addresses contextual and individual barriers to PrEP prescription to Black cis-gender women.

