**Procedures for Evaluating Proximal Implementation Outcomes:**

**Reach Outcome:** For this study outcome, Reach (i.e. the number of individuals who are willing to participate in an initiative) is defined as the absolute number of Black cis-gender women who receive a PrEP prescription. We will also evaluate the proportion of women prescribed PrEP who had a PrEP indication. PrEP indication will not be defined using the Center for Disease Control and Prevention (CDC) PrEP indication clinical guidelines due to evidence suggesting these criteria are too restrictive and may not predict risk. Instead we will define PrEP eligibility based on the CDC’s guidance summary criteria, deeming those PrEP eligible who meet any of the following criteria for cis-gender women not living with HIV (over a 6-month timeframe): HIV-positive sex partner, bacterial STI (gonorrhea or syphilis), more than one sex partner, inconsistent condom use, sex for exchange of goods, or being in a high-prevalence network. This data will be obtained based on the sexual risk screener (a component of implementation strategy) documented in the chart during patient visits.

**Procedures.** Data will be collected from the university’s electronic medical record, looking at visit data for all cis-gender women with clinic visits during the pilot timeframe. We will be able to extract prescription data directly, but PrEP eligibility and referral will require review of chart documentation.

**Preliminary Effectiveness Outcome:** To evaluate effectiveness of PrEP4Her, we will determine increases in PrEP prescriptions over-time. We will also evaluate what patient factors are associated with PrEP prescription.

**Procedures.** A data extraction of the UAB electronic medical record will be done (as described above) at 3-month time intervals after implementation of PrEP4Her (i.e. baseline, 3-months and 6-months’ time). We will collect the following patient demographics: age, race, ethnicity, and insurance status.

**Statistical analysis.** Frequencies for prescription will be reported overall and for each independent variable (i.e. patient demographics), at each of the 3 time points (baseline, 3 months and 6 months). Means, standard deviations and t-test comparisons between those referred and prescribed PrEP will be reported for continuous

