**Table 5. Potential Interview Topics grounded in Sekhon et al. Theoretical Framework**

	Constructs	Operationalized Topics
Prospective Acceptability: prior to participating in PrEP4Her	Affective Attitude	
 
Feelings about PrEP4Her
 

	Burden	
 
How much effort was required to participate in PrEP4Her
 

	Ethicality	
 
Did PrEP4Her align with your values
 

	Intervention Coherence	
 
How well did you understand PrEP4Her and how it worked
 

	Opportunity Costs	
 
How much values or perceived benefits were given up to engage in PrEP4Her
 

	Perceived Effectiveness	
 
How well did PrEP4Her achieve its purpose
 

	Self-efficacy	
 
Confidence in performing behaviors required to participate in PrEP4Her
 

Note: For Black cis-gender women, questions will be framed around the PrEP4Her implementation strategy that targeted patients.

**Data Analysis.** Drs. [name] and [name] will lead coding and the analytic approach. We will develop a preliminary codebook including *a priori deductive codes*, based on constructs from our theoretical framework, *inductive codes* that emerge from the data and *pattern codes* that connect concepts to one another. The coding team will code a sub-set of transcripts in parallel to compare coding and adjust codebook definitions until adequate inter-coder reliability is achieved.

**Feasibility:** We will measure whether PrEP4Her is appropriate for a larger, full-scale implementation trial by surveying out key-stakeholders prior to interviews (conducted to assess acceptability).

**Procedures.** Feasibility will be measured using the validated scale *Feasibility of Intervention Measure (FIM)* (Cronbach's alpha 0.85-0.91). This includes straightforward items such as "[PrEP4Her] was appealing to me", "[PrEP4Her] seemed suitable", and "[PrEP4Her] seemed easy to implement", which respondents rate on a 5-point Likert scale.

**Statistical Analysis:** Descriptive statistics, using medians and inter-quartile ranges and frequencies, will be calculated to characterize feasibility.

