**C6. Impact and Future Directions:** Upon completion of our Aims, we will have developed a culturally tailored strategy to improve uptake of PrEP among Black cis-gender women, ready for further testing. If PrEP4Her shows feasibility, acceptability and preliminary efficacy in enhancing PrEP uptake for Black cis-gender women, we will prepare a subsequent R01 application to conduct a fully powered, implementation science trial across multiple gynecological care sites across the South. Even in the absence of preliminary efficacy of the pilot, the knowledge gained around determinants and components to include in our PrEP4Her implementation strategy to integrate PrEP services into GYN settings will provide novel insights to inform future HIV prevention research among this highly impacted group.

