### **Procedures:**

- a. **Visit data for all cis-gender women with clinic visits during the pilot timeframe**
- b. **PrEP prescription data**

- c. **PrEP eligibility and referral data**
- 2. **Preliminary Effectiveness:** Defined by increases in PrEP prescriptions over time. We will also evaluate what patient factors are associated with PrEP prescription.

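### Preliminary effectiveness is an increase of unstated size from a stated baseline of zero, so any non-zero prescription count can be read as meeting the hypothesis; report prescribed women over indicated women with an exact interval

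*Combined protocol and SAP*

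**What the plan says.** - **Hypothesis (protocol C3):** PrEP services integrated into the clinic "will be feasible and acceptable, with an increase in PrEP prescription (currently zero prescriptions) for Black cis-gender women". Section B1 supports the zero: "to date, no patients seen at the pilot facility have been prescribed PrEP".
- **Preliminary effectiveness (protocol Aim 3):** "To evaluate effectiveness of PrEP4Her, we will determine increases in PrEP prescriptions over-time". The SAP (Paper 1, item 2) has the same definition: "Defined by increases in PrEP prescriptions over time". The protocol's analysis is frequencies at baseline, 3 and 6 months, plus a comparison of patient factors. Neither document gives a minimum increase, a confidence interval or a reference value.
- **Reach (protocol Aim 3; SAP Paper 1, item 1):** a count of Black women prescribed PrEP, with no target.
- **Go-forward statement (protocol C6):** "If PrEP4Her shows feasibility, acceptability and preliminary efficacy in enhancing PrEP uptake for Black cis-gender women, we will prepare a subsequent R01 application". C6 also allows for preliminary efficacy being absent, but does not say what result would count as absence.
- **Feasibility (protocol Aim 3):** "We will measure whether PrEP4Her is appropriate for a larger, full-scale implementation trial by surveying out key-stakeholders". The FIM scale is summarised by medians, interquartile ranges and frequencies. Acceptability comes from coded interviews. Neither has a cut-off.
- **Timing (SAP):** the SAP was started on September 26, 2025. It gives August 2024 as the end of the pilot and already lists 11 prescriptions.

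**The concern.** An increase with no stated size, measured from zero, separates results only into none and some. A single prescription in six months and wide uptake among women at risk could both be reported as preliminary effectiveness. That phrase matters because C6 makes it one of three conditions for preparing an application for a fully powered multi-site trial, and the other two conditions have no cut-off either.

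A count also has no denominator. The study's stated problem is that women with an indication do not receive PrEP, so the informative quantity is the share of indicated women who were prescribed it. Without that share, a reader of the primary paper cannot tell negligible coverage from useful coverage.

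**Working it through.** There is no figure in the plan to reproduce. Aim 3 states no sample size, power or threshold for prescribing; the only power calculation is for the Aim 1 provider survey.

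**Step 1. What the definition accepts.** With a baseline count of 0, a later count x is an increase whenever x ≥ 1. Only x = 0 clearly fails. The words about change over time leave some cases open, such as one prescription by month 3 and none afterwards, but they add no size requirement.

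**Step 2. Inputs for coverage.**
- Prescriptions: 11 (SAP, Quantitative data, items 1 and 7). Assumed to be 11 distinct women, all newly prescribed and all indicated, which is the most favourable reading.
- Records classified by indication: 4241 (SAP item 8). Taken here as women, although the item is also tabulated by visit date.
- Sexual health pre-screener: 1135 (SAP item 5). The screener is the declared source of eligibility.
- Share indicated: an assumption. The preference study in C2 found 28% eligible under CDC clinical guidelines. Aim 3 sets those guidelines aside as too restrictive, so the true share under the study's own criteria could be higher. A low value of 5% is shown for range.

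**Step 3. Number indicated.**
- 28% of 4241: 0.28 × 4241 ≈ 1187
- 28% of 1135: 0.28 × 1135 ≈ 318
- 5% of 4241: 0.05 × 4241 ≈ 212

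**Step 4. Coverage x/n with the exact (Clopper-Pearson) 95% interval.** The lower limit is the 0.025 quantile of Beta(x, n − x + 1). The upper limit is the 0.975 quantile of Beta(x + 1, n − x).
- 11/1187 = 0.93% (0.46% to 1.65%)
- 11/318 = 3.46% (1.74% to 6.11%)
- 11/212 = 5.19% (2.62% to 9.09%)

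The same 11 prescriptions meet the written definition in all three rows, while estimated coverage varies more than fivefold (5.19/0.93 ≈ 5.6).

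**Step 5. How easily x ≥ 1 is reached.** The chance is 1 − (1 − r)^n for a true rate r per visit. The right n is uncertain, so three are shown, each at r = 1 per 1000 and then r = 1 per 2000.
- n = 4161 (all visits, all patients, all periods; SAP item 1): 98% and 88%
- n ≈ 1664 (0.40 × 4161, assuming the 40% Black share in B1 applies): 81% and 56%
- n ≈ 613 (1664 × 7/19, also assuming the pilot is about 7 of 19 months with even volume): 46% and 26%

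The hypothesis concerns Black women in the pilot, so the smaller values of n are closer to it.

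**The case against.** The strongest reply is that this is a descriptive one-arm pilot. C3 states a directional expectation and itself describes an initial pilot needing further refinement. The expected outcome of Aim 3 is information to refine the strategy, no passage says that one prescription is success, and the only consequence in C6 is a grant application. This stands in part: a pilot need not be powered or have a formal test. It does not answer the point, because C6 still depends on preliminary efficacy being shown, and the only measure offered for it cannot grade the result.

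A second reply is that Reach already includes a proportion. Read as worded, its denominator is women who were prescribed PrEP, so it describes how well prescriptions were targeted and not how many indicated women were covered.

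Three stronger readings are tempting, and the documents do not support them.
- **The pilot could never show failure.** Zero prescriptions would fail. The zero baseline is also a proposal-time statement, and the SAP text does not say how the 11 prescriptions divide by period.
- **Almost any strategy would pass.** The 98% and 88% in Step 5 count all visits in all periods. For Black women in the pilot the chances may be as low as 46% and 26%.
- **The 11 prescriptions fall short of the national 4%.** Section A2 reports that "of the 468,000 cis-gender women with a PrEP indication, only 19,000 (4%) are currently receiving prescriptions" as background, not as a preset reference. It is a national prevalence of current prescriptions, not new prescribing at one clinic over some months. A4 and A3 of the background describe other settings, and A3 gives rival figures (6% of those referred using PrEP, 18% accepting referral). Choosing 4% now would mean choosing a pass mark with the 11 already known. It would also be severe: with 424 indicated women (10% of 4241, an assumption), a lower limit above 4% needs 26 prescriptions, and a strategy with true coverage of 5% would pass only 17% of the time. With 318 indicated, the interval of 1.7% to 6.1% spans 4% in any case.

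**Conclusion.** The concern holds in a limited form. Preliminary effectiveness is an increase of no stated size from a stated zero, so any non-zero count can be read as meeting the hypothesis, and none of the three conditions in C6 has a cut-off. The consequence is that the reported result is uninformative about coverage. It does not follow that PrEP4Her did poorly.

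The size of the problem is the spread in Step 4, from 0.9% to 5.2% of indicated women for the same 11 prescriptions. That spread rests on assumed denominators, on SAP totals whose units and periods differ, and on all 11 being distinct, newly prescribed and indicated. If some were not, coverage would be lower. If more than 28% were indicated under the study's broader criteria, it would also be lower. The documents give no basis for choosing one row, which is why the actual number of indicated women has to be reported.

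**What to change.** 1. In SAP Paper 1, item 2, do not present an increase from zero as evidence of preliminary effectiveness. Report distinct women newly prescribed PrEP over distinct women with a documented PrEP indication, by intervention period, overall and for Black women, each with an exact 95% interval. Base the effectiveness statement on that estimate and interval. First settle one definition of indication: the eligibility criteria in Paper 1, item 1 use a 6-month window, while item 8 of the quantitative data uses STI in the last 12 months and multiple partners.
2. State in the paper and in C6 that no progression threshold for prescribing, FIM or acceptability was set before the pilot, and that the SAP was started after the pilot ended. The decision to proceed is then a judgement and not a confirmed hypothesis.
3. Do not add a pass mark now. The national 4% may appear as descriptive context if it is labelled post hoc and not directly comparable.

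The cost is a little more analysis on data that the SAP already lists (items 7 and 8), including reducing visits to distinct women. No new patients or procedures are needed. The downside for the sponsor is that the claim may become less favourable.
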